## Statistical Considerations

An intent-to-treat (ITT) design was used wherein all participants were analyzed in the groups to which they were randomly assigned, regardless of treatment received or protocol deviations. The projected sample size was 112 participants a priori to reach a final sample of 80 randomized subjects (40 per group) to achieve 80% power to detect an effect size as small as 0.64,  $\alpha=0.05$ , two-tailed, for measures of the difference between LTGO and EUC groups in change in physical function, physical activity, and blood pressure control between baseline and 3 and 6 months.

Phases of data analysis involved an initial screening of data followed by the primary analysis to address each specific aim. All the analyses, including exploratory data analysis and linear mixed model, will be conducted by using SAS (v. 9.4, SAS Institute, Inc., Cary, NC).

Standard descriptive summaries (e.g., means, standard deviation, percentiles, range) and graphical techniques (e.g., histograms, scatter plots) were generated. The distribution of key variables was examined to ensure that the proposed modeling techniques were suitable. The assumptions underlying planned analysis methods were checked, and appropriate data transformation were performed, if necessary. The two groups were compared with respect to baseline variables using Student t-test or Mann-Whitney U test for continuous variables; categorical variables were compared between two groups by using Chi-square test or Fisher's exact test to ensure that randomization resulted in equal distribution of important variables.

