## Scientific Background

Lung transplantation is one of the fastest growing solid organ transplant procedures in the United States.[1] Over the past four decades, notable progress has been made in the success of lung transplantation due to advances in organ preservation, surgical techniques, availability of bridge treatments (e.g., ventilator support, extracorporeal membrane oxygenation), and new immunosuppressive regimens.[2] According to the most recent report from the International Society for Heart and Lung Transplantation (ISHLT), the overall 5-year survival rate for LTR is 53%. [2] Lung transplantation leads to extended survival and quality of life in persons limited by advanced lung disease[3-5] and, therefore, has become an established treatment option.

After transplant, lung function typically returns to near normal levels. [6-8] However, reduced physical function and an inactive lifestyle compromise this benefit. Prior to transplant, end-stage lung disease reduces ventilatory capacity.[9] Disabling dyspnea limits physical activity and exercise, causing low muscle mass and qualitative changes in large exercising skeletal muscle groups.[10] Thus, LTR are severely deconditioned when they come to transplant surgery. After transplant, skeletal muscle changes persist.[11] Side effects of immunosuppressive agents further reduce lean muscle mass, increase fatigue, and decrease motivation to stay active.[12] A systematic review of 18 studies evaluating loss of skeletal muscle mass, strength and function in LTR reported that quadriceps strength was reduced in the pre-transplant period (range, 49%-86% predicted; n = 455 patients), further reduced immediately after transplant (51%-72% predicted, n = 126), with variable improvement at 3 months after transplant (58%-101% predicted, n = 164).[13]

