While improved lung function after transplant has the potential to improve physical function, there is consistent evidence of limitations in reaching this goal.[6, 14-16] To promote rehabilitation goals, LTR are advised to attend a PR program.[17-19] Whereas post-transplant medical management requires following an established protocol, participation in PR is elective to LTR's individual decision. Studies documenting PR outcomes in other populations, [20, 21] consistent with our experience, report that PR is underused. It enrolls about a half of those referred [20] and loses > 25% of those who enroll to attrition.[21] Attrition of LTR in our PR clinic was greater than 50%. Barriers include scheduling and travel requirements,[18] perceptual disincentives and, of concern to LTR on immunosuppressive regimens, group participation which risks exposure to infection. Further, and of primary interest to this study, we pose that characteristics inherent to PR programs impact long-term adherence to exercise in LTR. During PR, exercise occurs under close clinician supervision but, afterward, LTR are expected to continue exercise unsupervised at home while not feeling confident. Consequently, LTR have little opportunity to establish behavior patterns that promote continued, independent self-management of exercise. Importantly, behavioral strategies, essential to achieve exercise goals and sustain self-management of exercise and active lifestyle, are not the main focus of traditional PR programs.

Telerehabilitation (TR) offers a flexible and sustainable alternative with the potential to promote and sustain self-management of exercise in LTR. Defined as an application of tele-health to rehabilitation,[22] TR uses telecommunication and computing technology to assess patients and deliver interventions in remote locations.[23-25] RCTs have evaluated TR-focused interventions in other populations, e.g., knee arthroplasty, stroke, and supported benefits of TR.[26-28] No

RCT has evaluated the use of the TR in LTR nor have exercise interventions for LTR incorporated behavioral strategies for self-management of exercise.

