## Study Design & Methods

After completing a baseline assessment, lung transplant recipients (LTRs) were randomized 1:1 to either the LTGO or Enhanced Usual Care group. To achieve balance between groups for known differences in exercise capacity, a blocked randomization scheme stratified by sex, and length of transplant-hospital stay ( $\leq 2$  weeks or  $> 2$  weeks) was used as an indicator of hospital-associated deconditioning. The statistician was responsible for randomization.

After the start of Covid, all study activities were performed remotely for both groups, including intervention delivery, recruitment, consenting, assessment, and data collection. Outcome assessors were blinded to group assignments. Data collectors were trained to perform study assessments until they demonstrated competency. Quality control checks of inter-rater reliability between assessors were repeated every quarter and remediation was instituted to remedy any drift from the assessment protocol less than ( $r = .97$ ). Assessors were trained to abstract data

from the electronic health record using established code books. Inter-rater reliability was determined between two raters for every 10 records. Data safety and intervention fidelity were monitored regularly. Surveys and semi-structured interviews were used to determine the usability and acceptability of the LTGO intervention. Performance of all assessments and delivery of intervention sessions and phone calls were audio or video-recorded. Intervention fidelity was monitored for 10% of phase 1 exercise sessions per subject and all phase 2 phone calls. Data safety monitoring (DSM) meetings were held monthly by the PI and PD, and annually by PI, PD and medical monitor.

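### Does 80% power from 80 randomised participants leave the trial short once some are lost before 3 or 6 months?

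*Combined protocol and SAP*

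**What the plan says.** In the combined protocol and SAP, the sample-size statement is one sentence in Statistical Considerations. It begins "The projected sample size was 112 participants a priori" and continues to "a final sample of 80 randomized subjects (40 per group) to achieve 80% power to detect an effect size as small as 0.64", at a 5% significance level, "two-tailed, for measures of the difference between LTGO and EUC groups in change" to 3 and 6 months. The same section adopts intention to treat and names the model: "All the analyses, including exploratory data analysis and linear mixed model, will be conducted by using SAS".

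Study Design & Methods fixes the point of randomisation: "After completing a baseline assessment, lung transplant recipients (LTRs) were randomized 1:1". It also says that, once Covid began, assessment and data collection were remote in both groups.

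The attrition figures are in the Scientific Background. Of pulmonary rehabilitation in other populations it says that it "loses > 25% of those who enroll to attrition". Of the team's own clinic it says "Attrition of LTR in our PR clinic was greater than 50"%. The same background states that "the overall 5-year survival rate for LTR is 53"%. No section gives an expected loss of outcome data after randomisation.

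**The concern.** The power is attached to the number randomised, not to the number with outcome data. If 112 people enter, 80 reach randomisation, and randomisation comes after baseline, then the margin of 32 is spent before follow-up starts. The design has almost no slack: by the exact t calculation, 79 of the 80 are needed for 80% power.

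Set against that, the only attrition figures in the document are large, and the power sentence does not mention them. If a quarter of those randomised had no 6-month data, the trial would be more likely to miss a true effect of 0.64 than the plan states. A null 6-month result would then be weaker evidence than a reader of the plan would think.

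**Working it through.** **Inputs.** Standardised effect d = 0.64, two-sided alpha 0.05, 40 per group, 112 projected and 80 final (Statistical Considerations); 1:1 allocation (Study Design & Methods). Loss rates below are assumptions, because the documents give none for outcome data.

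**1. The plan's own figure.** For a two-sample t-test with n per group, the noncentrality is d × √(n/2) on 2n − 2 degrees of freedom.
- n = 40: 0.64 × √20 = 2.86 on 78 df, power 80.7%. The stated 80% reproduces.
- Solving for 80% gives 39.31 per group.
- 40 + 39 gives 80.2%; 39 + 39 gives 79.7%.
- By the normal approximation, power at 40 per group is 81.7%, and a total of 77 still gives 80.2%.

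So 79 is the exact threshold, but it is a soft one: one or two losses cost about a point of power.

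**2. Complete-case power under assumed loss from 80.**

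| Assumed loss | With data | Power at 0.64 | Effect detectable with 80% power |
|---|---|---|---|
| 0% | 80 | 80.7% | 0.63 |
| 10% | 72 | 76.4% | not computed |
| 20% | 64 | 71.2% | 0.71 |
| 25% | 60 | 68.4% | 0.74 |

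**3. What the mixed model recovers at 6 months.** If a fraction f is lost only after month 3, and the 3- and 6-month changes have correlation r (assumed), the effective n per group is 40 / [1 + f/(1 − f) × (1 − r²)].
- f = 0.25, r = 0.5: 40 / (1 + 0.333 × 0.75) = 32.0, power 71%.
- f = 0.25, r = 0.8: 40 / (1 + 0.333 × 0.36) = 35.7, power 76%.

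Nothing is recovered for someone lost before month 3, so 68% remains the lower end at 25% loss.

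**4. The other reading of 112.** The reduction is (112 − 80)/112 = 28.6%, slightly more than the cited 25%. Keeping 79 with data at 25% loss needs 79/0.75 = 105.3, so 106 randomised. If 112 had been meant as the number entering follow-up, 112 × 0.75 = 84 would have data at 25% loss, and the plan would be covered.

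**5. Deaths.** At a constant rate (assumption), 53% survival at 5 years implies 1 − 0.53^0.1 = 6.15% mortality over 6 months, or 4.9 of 80. That leaves about 37.5 per group and 78% power. This is immaterial, and probably too pessimistic for participants who had been discharged and approved by the medical monitor.

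**The case for a change.** The strongest case for a change is that the wording is not really ambiguous. The sentence says 80 randomised, 40 per group, and randomisation follows baseline. If the authors meant 112 randomised and 80 completing, the sentence misdescribes the intention-to-treat population, so it needs correcting on either reading. The mixed model recovers only part of any loss, and a clarification would cost two or three sentences.

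Part of this stands. The plan does not say what 112 counts or what loss after randomisation was assumed, and on the literal reading 80% power needs nearly complete follow-up.

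The step from there to an underpowered trial does not stand. The cited attrition is people leaving rehabilitation programmes, and the 25% figure comes from other populations. Under intention to treat, a participant who stops exercising can still be assessed and analysed. The background blames scheduling, travel and infection risk in groups for poor uptake and retention, and offers telerehabilitation as the way round them. Remote assessment and mailed activity monitors remove much of the same burden from data collection. That is a reason, though not a number, to expect less loss. The 50% figure has no basis as a forecast of missing outcomes.

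**Conclusion.** No change follows. The stated calculation is correct for 80 participants with data, and nothing in the documents shows that outcome data would be lost at the rates cited for rehabilitation programmes. What remains is an undefined count (112) and an unstated assumption about follow-up.

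If there were loss after randomisation, its cost would be gradual: about 4 points of power at 10% (80.7% to 76.4%) and about 12 points at 25% with complete cases only (80.7% to 68.4%), with the mixed model recovering some of this at 6 months. These figures rest on assumed loss rates, on an unadjusted comparison of change scores for the complete-case values, and on an assumed correlation of 0.5 to 0.8 for the mixed-model values.

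Filling the gap would not alter the number randomised, the analysis or the estimates. The plan is written largely in the past tense, with randomisation described as done, so an allowance added now would serve no purpose. Analysts will in any case report how many participants have data for each outcome and visit, and the confidence intervals will show the precision achieved.

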## Protocol changes to primary outcomes due to COVID

1. Primary Outcome: Physical function-Walking, Change is being assessed from baseline to 3 months

\* Protocol modification 06-24-2020: since COVID, alternate measures for 6MWT due to inability to conduct in-person outcome assessments were the 30 Second Chair Stand Test (see primary outcome 5 and 6) and Average Steps per Day

2. Primary Outcome: Physical function- Walking, Change is being assessed from baseline to 6 months using Avg Steps per Day

\*Protocol modification 06-24-2020: since COVID, alternate measures for 6MWT due to inability to conduct in-person outcome assessments were the 30 Second Chair Stand Test (see primary outcome 5 and 6) and Average Steps per Day

3. Primary Outcome: Physical function- Balance-Change is being assessed from baseline to 3 months using the Berg Balance Scale

4. Primary Outcome: Physical function- Balance-Change is being assessed from baseline to 6 months using the Berg Balance Scale

5. Primary Outcome: Physical function- Lower Body Strength-Change is being assessed from baseline to 3 months using the 30 Second Chair Stand Test

6. Primary Outcome: Physical function- Lower Body Strength-Change is being assessed from baseline to 6 months using the 30 Second Chair Stand Test

Primary outcome: Physical function- maximal exercise watts per Kg, Change is being assessed from baseline to 3 months during the Cardio Pulmonary Exercise Test (CPET)

\*Protocol modification- since COVID, the max ex watts per KG test was excluded from outcomes due to inability to conduct in-person outcome assessments and no alternative measure was available for the CPET. This modification does not appear in the primary outcomes change history.

\* Protocol modification-Physical function- Quadriceps Muscle Strength-outcome was never assessed as it was deemed redundant with the 30 Second Chair Stand Test. This modification does not appear in the primary outcomes change history.

7. Primary Outcome: Physical function- Respiratory-related quality of life, Change is being assessed from baseline to 3 Months using the St. George Respiratory Questionnaire (SGRQ)

8. Primary Outcome: Physical function- Respiratory-related quality of life, Change is being assessed from baseline to 6 Months using the St. George Respiratory Questionnaire (SGRQ)

9. Primary Outcome: Physical Activity-Minutes of Moderate to Vigorous Physical Activity Per Day, Change from Baseline to 3 Months using Actigraph

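### The linear mixed model has no stated terms, and baseline enters only through the change score; conditioning on baseline and adding the randomisation strata would cost little and could gain precision

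*Combined protocol and SAP*

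**What the plan says.** All references are to the combined protocol and SAP.

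- **Outcomes.** The section on COVID-related changes to the primary outcomes words them as change from baseline to 3 and to 6 months, for example "Change is being assessed from baseline to 3 months using the 30 Second Chair Stand Test".
- **Power.** Statistical Considerations claims "80% power to detect an effect size as small as 0.64" with 40 per group, two-sided alpha 0.05, "for measures of the difference between LTGO and EUC groups in change in physical function" and the other domains. It does not say which SD the 0.64 is divided by.
- **Model.** The only mention is "All the analyses, including exploratory data analysis and linear mixed model, will be conducted by using SAS". No response, fixed effects, covariates or covariance structure is given.
- **Randomisation.** Study Design & Methods states "After completing a baseline assessment, lung transplant recipients (LTRs) were randomized 1:1", and describes the scheme as one to balance the groups "for known differences in exercise capacity, a blocked randomization scheme stratified by sex, and length of transplant-hospital stay" (up to 2 weeks, or longer). No later section puts either factor in the model.
- **Baseline comparisons.** Groups are compared on baseline variables by significance tests "to ensure that randomization resulted in equal distribution of important variables". No action follows from the results.

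**The concern.** At least two different analyses fit this wording:

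- **(a)** A change score, or a mixed model for all three visits with a separate baseline mean in each arm. With complete data these give the same treatment contrast.
- **(b)** A model that conditions on baseline, either as a covariate or as a first measurement whose mean is constrained equal across arms.

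Both are valid in a randomised trial, but their precision can differ. The plan's emphasis on change points towards (a) without excluding (b). At stake is whether the trial gets the most from a baseline assessment it already holds, and whether a reader can tell which model produces the main results. Similarly, the plan treats sex and hospital stay as related to exercise capacity when randomising, but does not carry them into the model.

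**Working it through.** **Inputs from the documents:** 40 per group, effect size 0.64, two-sided alpha 0.05, 1:1 allocation.

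**Assumptions, because the documents give no value:** the baseline-to-follow-up correlation rho (0.3 to 0.9), the ratio k of follow-up SD to baseline SD (0.8 to 1.4), and the SD unit of 0.64. Normal outcomes and complete data are also assumed.

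**1. The plan's own figure.** A two-sample t comparison with d = 0.64, 40 per arm and 78 df has power 80.7%. The detectable effect at 80% power is 0.634. The stated figure is reproduced without any baseline or strata term.

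**2. Variance comparison.** With baseline SD set to 1:

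- change score: 1 + k² − 2·rho·k
- conditional on baseline: (1 − rho²)·k²
- difference, (a) minus (b): (1 − rho·k)²

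The difference is a square, so (b) is never worse asymptotically, and the two are equal when rho·k = 1. The ratio (b)/(a) is (1 − rho²)k² / (1 + k² − 2·rho·k), which is (1 + rho)/2 when k = 1.

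**3. A mixed model does not by itself deliver (b).** Take generalised least squares with three visits, SDs 1, k, k and a common correlation. At rho 0.5 and k 0.8, the contrast has variance 0.84 × 2/40 = 0.0420 with free baseline means and 0.48 × 2/40 = 0.0240 with constrained means, a ratio of 0.571. At rho 0.7 and k 1.4, both are 0.0500.

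**4. Power if 0.64 is in SD-of-change units.** Power under (a) is 80.7% throughout. Power under (b) is the noncentral t at 0.64/√ratio with 75 df (80 participants less intercept, group, baseline, sex and stay). Each cell shows the variance ratio, then power under (b).

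| k | rho 0.3 | rho 0.5 | rho 0.7 | rho 0.9 |
|---|---|---|---|---|
| 0.8 | 0.50; 97.9% | 0.57; 96.2% | 0.63; 94.6% | 0.61; 95.2% |
| 1.0 | 0.65; 93.9% | 0.75; 90.4% | 0.85; 86.5% | 0.95; 82.6% |
| 1.2 | 0.76; 89.9% | 0.87; 85.7% | 0.97; 82.0% | 0.98; 81.5% |
| 1.4 | 0.84; 86.9% | 0.94; 82.9% | 1.00; 80.7% | 0.85; 86.7% |

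Simulation (12,000 replicates, k = 1) gave 93.4, 90.6, 86.2 and 81.7% under (b). Size was 0.047 to 0.052 for both analyses in every cell simulated.

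**5. If 0.64 is in baseline-SD units instead (k = 1).** Power is 67, 81, 95 and over 99% under (a), and 84, 90, 98 and over 99% under (b), at rho 0.3, 0.5, 0.7 and 0.9.

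**6. What the strata add.** If they explain an assumed 10 to 20% of the outcome level, they remove a further 4 to 8% of residual variance after baseline at rho 0.5, and 2 to 4% at rho 0.7 (k = 1).

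**7. Cost when nothing is gained.** At rho 0.7 and k 1.4, with strata that explain nothing, simulated power went from 80.5% to 80.1%. If all three covariates are left to chance imbalance, the expected variance inflation is 1 + 3/74, and power is 79.1%. That is an average. At the 95th percentile of joint imbalance the inflation is about 1.11, and power falls to between 76% and 77%.

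**8. Baseline tests.** At 40 per arm, a difference reaches p < 0.05 only above t(0.975; 78) × √(2/40) = 0.445 SD. A non-significant test does not establish balance.

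**The case against.** Several counter-arguments have force.

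- **Change scores already use baseline.** This is correct. At k = 1 the change-score variance relative to follow-up alone is 2(1 − rho), that is 0.60 at rho 0.7 and 0.20 at rho 0.9. A reader might infer that the trial discards its baseline data, but the outcome definitions contradict that. The gap is only that baseline is not stated as a covariate or a constrained first measurement.
- **The gain cannot be established.** This stands. The variance ratio runs from 0.50 to 1.00 over the grid, and nothing in the documents locates the trial within it. The table shows a range and is not a forecast.
- **The strata were not tested by simulation.** They were set to explain nothing, so the simulated size says nothing about leaving out prognostic strata. The figures in step 6 rest on an assumed share of variance.
- **The analysis may be finished.** Most of the text is in the past tense, and only the software sentence looks ahead. If so, the model can no longer be fixed in advance.
- **Terms may be set elsewhere.** The section alludes to proposed modelling techniques, so a fuller specification may exist outside the public document. That limits confidence, but the plan as published still does not secure the adjustment.
- **The baseline tests change nothing.** Agreed: no decision depends on them.

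**Conclusion.** The point holds as a modest efficiency recommendation. The published plan names a mixed model without terms, lets baseline in only through the change score, and does not bring the strata into the model. Conditioning on baseline is asymptotically never less precise with complete data. With 0.64 in SD-of-change units and equal SDs, power would go from 80.7% to roughly 83 to 94%. With rho 0.7 and k 1.4 it would not move. The correlation, the SD ratio and the SD unit are all assumptions.

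A reader might go further and infer that the trial is biased, that its type I error is inflated, that it is underpowered, or that the plan rules out adjustment. The documents support none of these. A randomised comparison of change scores is unbiased over repeated randomisations, the sample size is correct for its stated inputs, and the text is silent on adjustment. The figures apply to the continuous outcomes only, and do not carry over to change in stage of hypertension, which is ordinal.

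**What to change.** For each continuous outcome, specify a mixed model with:

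- the outcome at baseline, 3 and 6 months;
- visit and group-by-visit terms, with baseline means constrained equal across arms (or 3- and 6-month outcomes with baseline as a covariate);
- sex and hospital-stay stratum;
- the group contrasts at 3 and at 6 months as the reported effects.

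The constrained form also keeps anyone who lacks a baseline value on a given outcome. The plan allows that "appropriate data transformation were performed, if necessary"; where this applies, transform the baseline in the same way. If the analysis is already complete, state the model that was fitted and report this one as a sensitivity analysis.

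**Cost.** A paragraph of SAP text and a few lines of SAS code. The plan places the baseline assessment before randomisation, and the strata were needed to randomise. The statistical price is about 3 degrees of freedom. If the covariates explain nothing beyond the change score, it is also about 1 to 2 points of power on average (80.7% to about 79 to 80%), and more in an unusually imbalanced sample.

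**Minor reporting point.** Present baseline characteristics descriptively, without significance tests. This alters no result.
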